7.5 Sample Size Calculation

Deleted finasteride arm (n = 35) and related text.

Deleted Finasteride versus Placebo column from Table 2.

Removed finasteride arm.

Study Entry

8.4 Instructions for the Subjects

8.6 Compliance With Protocol

10.5.1 Labeling/Packaging

Changed time subject has entered the study from time of randomization (Day 1) to screening.

Deleted instructions for finasteride group.

Deleted finasteride bottle information.

Deleted finasteride information.

Correction as informed consent form is signed at screening.

Removed finasteride arm.

See rationale above.

See rationale above.

ALLERGAN

Protocol 1922-201-002 Amd 1

Date (DD/MMM/YYYY)/Time (PT) Signed by: Justification

2.2 List of Figures

3. List of Abbreviations and Definition of Terms

Table 3-1 Abbreviations and Definitions of Terms

Term/Abbreviation	Definition
AE	adverse event
AGA	androgenetic alopecia
ALT	alanine aminotransferase
ANCOVA	analysis of covariance
ASA	Alopecia Symptom Assessment
AST	aspartate aminotransferase
$AUC_{0\text{-inf}}$	area under the concentration-time curve from time 0 to infinity
BID	twice daily
bpm	beats per minute
CMH	Cochran-Mantel-Haenszel
CSR	Clinical Study Report
eCRF	electronic case report form
LOCF	last observation carried forward
mITT	modified intent-to-treat
NHS	Norwood-Hamilton Hair Loss Scale
PT	preferred term

SOC system organ class
SSA Subject Self-Assessment

TAHC target area hair count

TBL total bilirubin

ULN upper limits of normal
WBC white blood cell

4. Introduction

This document details the planned analysis for Study 1922-201-002, a phase 2A study to evaluate the safety, tolerability and efficacy of oral administration of setipiprant tablets 1000 mg twice daily (BID) in males with androgenetic alopecia (AGA) who are 18 to 49 years old and in generally good health. Specifications of tables, figures, and data listings are contained in a separate document.

The statistical analysis will be conducted after all subjects have completed or exited the study and after database lock.

4.1 Primary Study Objectives and Design

The objectives of this study are to evaluate the safety, tolerability, and efficacy of oral administration of setipiprant tablets 1000 mg BID in males with androgenetic alopecia (AGA), Male

subjects aged 18 to 49 years (inclusive) at baseline, who are in general good health, have androgenetic alopecia with vertex patterns IIIv, IV, or V on the NHS, and are dissatisfied with

[figure not shown]
will be screened for eligibility for enrollment into the study.

All investigators, site staff, and subjects will be blinded to whether subjects receive setipiprant or matching placebo during the study.

Approximately 152 subjects will be enrolled in up to 20 US sites. On Day 1, 140 eligible subjects will be randomly assigned to 1 of 2 treatment groups in a 1:1 ratio to receive setipiprant tablets 1000 mg BID (hereafter referred as Setipiprant), or placebo BID (hereafter referred as Placebo), and

will be stratified by baseline age group

(< 35 and \ge 35 years). Overall, the number of subjects enrolled into the setipiprant and placebo groups will be about 80 and 72, respectively (Figure 4-1).

This SAP is based on the Amendment 1 of the protocol. The original protocol had three treatment arms – Setipiprant 1000 mg BID, Placebo BID and Finasteride 1 mg QD. The Finasteride 1 mg QD was removed from Amendment 1 of the protocol. Data in the Finasteride group will be summarized but not compared with the other treatment groups.

5. Statistical Methodology and Study Endpoints

5.1 Statistical Methods Planned in the Protocol and Determination of Sample Size

This statistical analysis plan (SAP) will be approved prior to database lock. The SAP expands the statistical section of the protocol and contains a detailed description of methods to analyze data collected in the study. The text portion of the SAP will be included in the CSR report as Appendix 16.1.9.

5.1.1 Statistical and Analytical Plans

Statistical analyses will be conducted using

5.1.1.1 Common Conventions

5.1.1.1.1 Analysis Populations

Two populations will be used in the analysis: modified intent-to-treat (mITT) and safety.

The mITT population, consisting of all randomized subjects who have a baseline and at least 1 postbaseline measurement for 1 of the coprimary efficacy measures, will be used for analyses of efficacy data based on the randomized treatment group. All efficacy variables will be summarized and analyzed using the mITT population. Demographic and baseline characteristics will also be based on mITT population.

The safety population, consisting of all subjects who receive at least 1 dose of study drug (ie, all treated subjects), will be used for analyses of all safety data based on the actual treatment received.

5.1.1.1.2 Study Treatments

The following treatment groups are defined for this study.

- Setipiprant
- Placebo
- Finasteride: enrolled under the original protocol, data will be summarized but not included in any data analysis models.

They will be labeled as "Setipiprant", "Placebo" and "Finasteride" in the data summary tables/listings.

5.1.1.1.3 Statistical Methodology

The methodologies defined below apply as specified to individual endpoints defined in this SAP. Finasteride subjects enrolled prior to Protocol Amendment 1 will be summarized alone and will not be included in the analysis models. All statistical testing will be based on 2-sided hypothesis tests with a statistical significance of $p \le 0.05$, unless specified otherwise.

- Descriptive statistics include the sample size (N), mean, standard deviation (SD), median, minimum (Min), and maximum (Max) for continuous/ordinal data, and the sample size (N), frequency count, and percentage for categorical data.
- For the analysis of ordinal-scaled categorical data, unless specified otherwise, Cochran-Mantel-Haenszel (CMH) row mean scores test stratified by age group (< 35 and ≥35 years) will be used.
- Change from baseline (CFB) will be analyzed using an analysis of covariance (ANCOVA) model with treatment as a fixed effect and age and baseline value as covariates (if applicable). The treatment difference (Setipiprant versus Placebo) will be constructed based on the ANCOVA model, along with the 2-sided p-value and 95% confidence intervals (CI). The type III sums of squares will be used for all ANCOVA models.

5.1.1.4 Other Common Conventions

- The baseline value of an assessment will be the last value recorded prior to the subject receiving the first dose of study medication (day 1), except for TAHC, For these parameters, the baseline value is based on the nominal Visit 2 (baseline) macrophotography, which may include photos taken after the first dose of study drug when a reshoot was required to obtain evaluable baseline measurements.
- In general, change from baseline is calculated as follow-up minus baseline. Between-group differences will be calculated for Setipiprant minus Placebo.
- Clinical laboratory system will be presented with Standard International (SI) units.
- Medical Dictionary of Regulatory Activities (MedDRA) nomenclature will be used to code
 diagnosis or symptoms from medical histories, adverse events (AEs), indications for prestudy
 and concomitant medications. In addition, the Drug Dictionary Enhanced (DDE) preferred
 drug names from World Health Organization (WHO) Drug Dictionary will be used to classify
 all prestudy and concomitant medications by drug class and drug names.

5.1.1.2 Demographics and Other Baseline Characteristics

Disposition and exit status, demographics and baseline characteristics will be performed on the mITT population.

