2.2 Clinical Hypotheses

- Setipiprant tablets 1000 mg BID have an acceptable safety profile following oral administration for 24 weeks.
- Setipiprant tablets 1000 mg BID are more effective than placebo in increasing hair growth, as measured by the change from baseline in target area hair count (TAHC) of terminal hairs (1 cm² circular area) using digital image analysis at 24 weeks after oral administration.
- Setipiprant tablets 1000 mg BID are more effective than placebo in increasing scalp hair growth, as measured by the distribution of Subject Self-Assessment (SSA) scores using a 7-point scale at 24 weeks after oral administration.

3. Study Design

[figure not shown]
This is a multicenter, randomized, double-blind, placebo-controlled study with an active comparator group designed to determine the effect of treatment with setipiprant tablets 1000 mg BID on scalp hair growth as assessed by objective (ie, imaging-based) and subjective (ie, investigator- and subject-reported) measures.

All investigators, site staff, and subjects will be blinded to whether subjects receive setipiprant or matching placebo during the study.

Subjects must complete all screening and baseline procedures and meet all eligibility requirements to qualify for enrollment and randomization on Day 1 when they will be randomly

assigned to 1 of 2 treatment groups (setipiprant or placebo). All subjects will self-administer the assigned study drug over a 24 week period to evaluate the safety and effects on hair growth. After randomization, subjects will return to the research facility at Weeks 24 for protocol-defined efficacy and/or safety assessments and procedures, confirmation of compliance with study drug usage, and new study drug dispensation (except for Week 24). A follow-up visit will occur at Week 32 (ie, 8 weeks posttreatment) or the early exit visit for protocol-defined efficacy and safety evaluations and procedures.

Safety and efficacy assessments and study procedures are outlined in the Study Design and Schedule of Assessments (Table 1). The SSA will be evaluated at Weeks 24, and 32 (or early exit visit) using the subject's paired and randomly blinded screening (the screening photograph is defined as the subject's baseline) and postbaseline photographs, and at Weeks 24 and 32 (or early exit visit) using the subject's paired, unblinded screening and postbaseline photographs.

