7.4 Other Analyses

Subject disposition, demographic data, and variables relating to the conduct of the study (eg, number of subjects attending each visit) will be summarized overall and by treatment. All data will be listed. The number of subjects enrolled will be summarized, overall and by treatment

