5.1.1.2.1 Disposition and Exit Status

Subject disposition and exit status will be summarized overall and by treatment group using frequency distributions at the primary efficacy endpoint of week 24 as well as at the end of the study.

Reasons for early termination include AEs, lack of efficacy as determined by investigator, lost to follow-up, personal reasons, protocol violation, and other reasons. Subjects who discontinue prematurely will be listed along with the corresponding reason(s) for their early termination.

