5.1.1.3.1 Collection and Derivation of Primary and Other Efficacy Measurements

The coprimary efficacy variables will be based on the following 2 measures: TAHC within a 1 cm² circular area on the left side of the scalp and SSA.

• The TAHC is a standardized objective quantification of each subject's number of terminal hairs (hair width $\geq 30 \ \mu m$) within a 1 cm² target circular area on the left side located at the anterior leading edge of the vertex thinning area of the scalp using digital image analysis.

[figure not shown]
• The SSA score is the subject's assessment of change of hair growth, scored on a 7-point scale (-3 = greatly decreased, -2 = moderately decreased, -1 = slightly decreased, 0 = remained the same, +1 = slightly increased, +2 = moderately increased, and +3 = greatly increased). The analyses of the SSA from the blinded photograph assessments will be based on the actual change from the screening photographs (ie, if the postbaseline photograph is used as Photo A, the assessment score will be reversed for analyses).

[figure not shown]
The coprimary efficacy endpoints based on the measurements of TAHC and SSA (blinded) are the following.

[figure not shown]
- Change from baseline in TAHC within a 1 cm² target circular area on the left side located at the anterior leading edge of the vertex thinning area of the scalp at Week 24
- Subject Self-Assessment of change from baseline in hair growth as viewed on the subject's paired (before and after presented in a blinded fashion) global photographs of the vertex target area at Week 24 and measured by the distribution of SSA scores

[figure not shown]
Postbaseline evaluations of TAHC and SSA will be made at Week 24 and 32, with the primary analysis timepoint being Week 24. For SSA, if the postbaseline photograph is used as Photo A, then the assessment score will be reversed for analyses.

For each of the 2 coprimary measures (TAHC and SSA), missing data will be imputed up to Week 24 using last observation carried forward (LOCF) method.

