6.5 Imputation of Primary Efficacy Measurements (TAHC and SSA)

Missing data of all TAHC endpoints and SSA (blinded and unblinded) will be imputed up to Week 24 using last observation carried forward (LOCF) as follows: when there is no observation in a particular visit window, the latest non-missing observation prior to that visit window will be carried forward and used for analysis for that particular window, whether from a scheduled or unscheduled visit. Imputation will be applied to postbaseline visits up to Week 24 only. If missing data occur at scheduled visit(s) immediately following baseline, the baseline value will be carried forward for imputation. Analyses of Week 32 data will be based on observed cases without data imputation.

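### Disposition and exit reasons are tabulated on the mITT population, which leaves out randomized subjects who exit without a postbaseline TAHC or SSA; the SAP also moves demographics off the protocol's population without recording it

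*SAP*

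**What the plan says.** SAP Section 5.1.1.2 sets the population for a group of descriptive tables: "Disposition and exit status, demographics and baseline characteristics will be performed on the mITT population". SAP Section 5.1.1.1.1 defines mITT as "all randomized subjects who have a baseline and at least 1 postbaseline measurement for 1 of the coprimary efficacy measures".

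SAP Section 5.1.1.2.1, which falls under that rule, plans frequency tables of disposition and exit status, overall and by group, at Week 24 and at the end of the study. It continues: "Reasons for early termination include AEs, lack of efficacy as determined by investigator, lost to follow-up, personal reasons, protocol violation, and other reasons". It also plans a listing: "Subjects who discontinue prematurely will be listed along with the corresponding reason(s) for their early termination".

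On when the measurements exist, SAP Section 5.1.1.3.1 says "Postbaseline evaluations of TAHC and SSA will be made at Week 24 and 32". Protocol Section 3 adds an early exit assessment for the SSA: "The SSA will be evaluated at Weeks 24, and 32 (or early exit visit". Protocol Section 6.4.2 does the same for global photographs.

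Protocol Section 7.4 plans disposition, demographics and study-conduct summaries without restricting them to mITT ("number of subjects attending each visit) will be summarized overall and by treatment. All data will be listed"), and it adds the number enrolled by treatment.

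On demographics, Protocol Section 7.1 puts every subject who took at least one dose into the demographic summaries. SAP Sections 5.1.1.1.1 and 5.1.1.2 use mITT instead. SAP Section 5.2.2 reports no changes to the planned analyses.

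**The concern.** A disposition table should account for everyone randomized. Here, entry to the table depends on having stayed, or returned, long enough to give a postbaseline TAHC or SSA, so membership depends on the outcome being tabulated. A subject lost to follow-up who attends no exit visit is the clearest case: he leaves both the numerator and the denominator, so that exit reason is especially likely to be undercounted.

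Efficacy is analyzed on mITT with last observation carried forward. A reader therefore needs to know how many randomized subjects were left out of mITT, from which arm and why. No readable section of either document plans that count by reason.

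The report may also disagree with itself. SAP Section 5.1.1.4.2 tabulates adverse events leading to treatment discontinuation on the safety population. A treated subject who leaves for an adverse event without a postbaseline measurement would count there, but not under the adverse event reason in the disposition table.

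**Working it through.** **Who is excluded.** mITT requires an actual postbaseline measurement of TAHC or SSA. The carry-forward rule in SAP Section 6.5 ("Imputation will be applied to postbaseline visits up to Week 24 only") fills in values for analysis; it does not supply the measurement that the definition asks for. On the readable schedule, the excluded group is mainly subjects who leave before Week 24 and miss the early exit assessment. A leaver measured at an exit visit stays in mITT.

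**Inputs.** Planned numbers are 80 setipiprant and 72 placebo, 152 in total (Protocol Section 4.1). The readable text gives no dropout rate and no count of unmeasured leavers, so there is no figure in the plan to reproduce. All dropout inputs below are assumptions. Overall means setipiprant plus placebo; the earlier finasteride subjects are left out.

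**Formula.** Let N be randomized, D dropouts, d dropouts with neither measurement, and c completers with neither. Then

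- true rate = D/N
- rate shown on mITT = (D − d)/(N − d − c)

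The shown rate is below D/N when N(D − d) < D(N − d − c), that is, when d/(d + c) > D/N.

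**By arm.** Assume D = 16 of 80 (20.0%) and 14 of 72 (19.4%), a true difference of +0.6 points, with c = 0.

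| d, setipiprant v placebo | Setipiprant shown | Placebo shown | Difference (points) |
|---|---|---|---|
| 5 v 0 | 11/75 = 14.7% | 14/72 = 19.4% | −4.8 |
| 4 v 1 | 12/76 = 15.8% | 13/71 = 18.3% | −2.5 |
| 3 v 2 | 13/77 = 16.9% | 12/70 = 17.1% | −0.3 |
| 2 v 3 | 14/78 = 17.9% | 11/69 = 15.9% | +2.0 |
| 1 v 4 | 15/79 = 19.0% | 10/68 = 14.7% | +4.3 |
| 0 v 5 | 16/80 = 20.0% | 9/67 = 13.4% | +6.6 |
| 2 v 2 | 14/78 = 17.9% | 12/70 = 17.1% | +0.8 |

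With five unmeasured leavers, the overall rate shown is 25/147 = 17.0% against a true 30/152 = 19.7%. With an equal loss of 2 v 2 it is 26/148 = 17.6%, with almost no distortion between arms. The error can also run upward: if the only exclusions are five completers without usable measurements (d = 0, c = 5), the table shows 30/147 = 20.4%.

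**Wider range, overall rate.** N = 152, c = 0, with the unmeasured share rounded to whole subjects.

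| True rate | None unmeasured | A quarter | Half | Three quarters |
|---|---|---|---|---|
| 15/152 = 9.9% | 9.9% | 11/148 = 7.4% | 7/144 = 4.9% | 4/141 = 2.8% |
| 30/152 = 19.7% | 19.7% | 22/144 = 15.3% | 15/137 = 10.9% | 8/130 = 6.2% |
| 46/152 = 30.3% | 30.3% | 34/140 = 24.3% | 23/129 = 17.8% | 12/118 = 10.2% |

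**Demographics.** Protocol Section 7.1 assigns demographic summaries to subjects with at least one dose; SAP Sections 5.1.1.1.1 and 5.1.1.2 assign them to mITT. Neither SAP Section 5.2.2 nor the SAP's two amendment summaries mentions the move. No effect can be calculated for this part.

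**The case against.** The case against rests on five points.

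- **Exit reasons.** The sentence in SAP Section 5.1.1.2 does not name reasons for early termination, and the only output that Section 5.1.1.2.1 explicitly ties to reasons is a listing with no stated population. However, the reasons stand under the disposition and exit status heading, which Section 5.1.1.2 puts on mITT. Tabulating them on mITT is the natural reading.
- **Adverse event mismatch.** Stopping study drug and leaving the study are different events; Protocol Section 8.8 separates them. The two tables could differ on any population. This stands: using all randomized subjects removes one source of disagreement but does not guarantee agreement.
- **Size of the group.** Parts of the visit schedule cannot be read. Protocol Section 6.3.6 shows visits from Week 8, and the wording of SAP Section 6.5 suggests efficacy assessments before Week 24. If so, the excluded group is smaller. This stands, and it limits the size but does not change the rule.
- **Recoverability.** Enrolled counts and visit attendance by treatment are planned, adverse event discontinuations are tabulated on the safety population, and early exits are listed with reasons. Much could be rebuilt, so the gap is mainly in tabulated exits for other reasons. A reader should not have to rebuild a disposition table from listings.
- **No contradiction on disposition.** Protocol Section 7.4 names no population, and the SAP leaves table specifications to a separate document. Both are true. This part is a poor choice of population rather than a conflict, and the specifications would be expected to follow the SAP as written.

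**Conclusion.** The concern holds. Followed as written, the SAP removes unmeasured leavers from both the numerator and the denominator of the disposition table. The size is unknown. Under the assumed 20.0% v 19.4% dropout with five unmeasured leavers, the overall rate falls by 2.7 points (19.7% to 17.0%), and the difference between arms can shift in either direction. Across assumed dropout of about 10% to 30%, with a quarter to three quarters of leavers unmeasured, the overall rate is understated by roughly 2 to 20 points. The effect is zero if every leaver is measured and no completer is excluded.

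The demographics departure is real but minor. Both parts concern reporting: no endpoint, estimate or hypothesis test changes.

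**What to change.** In SAP Sections 5.1.1.2 and 5.1.1.2.1, tabulate disposition, exit status and reasons for early termination on all randomized subjects by randomized arm. Add a row giving the number excluded from mITT by arm and reason. Carry the same population into the separate table specifications.

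Present demographics on the safety population as Protocol Section 7.1 has it, keeping the mITT tables as supportive, or keep mITT and record the departure in SAP Section 5.2.2.

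The cost is a few sentences of SAP text and a changed population flag in a few descriptive tables. No new data or model is needed. The one downside for the sponsor is that the reported dropout rate may look less favourable.

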5.1.1.2.1 Disposition and Exit Status

Subject disposition and exit status will be summarized overall and by treatment group using frequency distributions at the primary efficacy endpoint of week 24 as well as at the end of the study.

Reasons for early termination include AEs, lack of efficacy as determined by investigator, lost to follow-up, personal reasons, protocol violation, and other reasons. Subjects who discontinue prematurely will be listed along with the corresponding reason(s) for their early termination.

5.1.1.2.2 Protocol Deviations

[figure not shown]
Significant (major) protocol deviations will be summarized using standard text by treatment group, and data listing will be presented.

5.1.1.2.3 Demographics

Demographic data will include age, sex, race, and ethnicity. Age will be summarized with descriptive statistics by treatment group and overall (ie, all treatment groups combined). In addition, age will be classified into categories of < 35 and ≥ 35 years, and race will be classified as White and non-White. Age group, sex, race and ethnicity will be summarized with frequency distribution by treatment group and overall, respectively.

5.1.1.2.4 Baseline Characteristics

Body mass index (BMI) is defined as weight (kg) / height (m)². Weight, height, and BMI will be summarized with descriptive statistics by treatment group and overall.

Distribution of subject's score of modified Norwood-Hamilton Scale of male-pattern baldness at baseline, Fitzpatrick skin type, Hair Loss history, and the Hair Satisfaction Assessment scale (HSA) will be presented with frequency distributions by treatment group and overall, respectively.

A subject listing with demographics and baseline characteristics will be presented.

